**Phase I/II Oncology liver chemistry increased monitoring criteria with continued therapy**

Liver Chemistry Increased Monitoring Criteria – Liver Monitoring Event	
Criteria	Actions
ALT $\geq$ 3xULN but <5xULN and bilirubin <2xULN, without symptoms believed to be related to liver injury or hypersensitivity and who can be monitored weekly for 4 weeks	
 
Notify the GSK medical monitor within 24 hours of learning of the abnormality to discuss subject safety.
 
Subject can continue study treatment
 
Subject must return weekly for repeat liver chemistries (ALT, AST, alkaline phosphatase, bilirubin) until they resolve, stabilise or return to within baseline
 
If at any time subject meets the liver chemistry stopping criteria, proceed as described above
 
If, after 4 weeks of monitoring, ALT <3xULN and bilirubin <2xULN, monitor subjects twice monthly until liver chemistries normalize or return to within baseline.
 

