***Attribution of Toxicity:***

When study interventions are administered in combination, attribution of an adverse event to a single component is likely to be difficult. Therefore, while the investigator may attribute a toxicity event to the combination, to belantamab mafodotin alone, or to pembrolizumab alone, for adverse events listed in [Table 5](#), both interventions must be held according to the criteria in [[Table 5](#)].

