Immune-related AEs	Toxicity grade or conditions (CTCAEv4.03)	Action taken to pembrolizumab	irAE management with corticosteroid and/or other therapies	Monitor and follow-up
				sufficient oral fluid intake is not feasible, fluid and electrolytes should be substituted via IV infusion.
AST / ALT elevation or Increased Bilirubin	Grade 2 	Withhold	
 
Administer corticosteroids (initial dose of 0.5 to 1 mg/kg prednisone or equivalent) followed by taper
 
	
 
Monitor with liver function tests (consider weekly or more frequently until liver enzyme value returned to baseline or is stable)
 

	Grade 3  or 4 	Permanently discontinue	
 
Administer corticosteroids (initial dose of 1 to 2 mg/kg prednisone or equivalent) followed by taper
 
	
Type 1 diabetes mellitus (T1DM) or Hyperglycemia	New onset T1DM or Grade 3 or 4 hyperglycemia associated with evidence of $\beta$ -cell failure	Withhold 	
 
Initiate insulin replacement therapy for subjects with T1DM
 
Administer an antihyperglycemic in subjects with hyperglycemia
 
	
 
Monitor subjects for hyperglycemia or other signs and symptoms of diabetes.
 

Hypophysitis	Grade 2	Withhold	
 
Administer corticosteroids and initiate hormonal replacements as clinically indicated.
 
	
 
Monitor for signs and symptoms of hypophysitis (including hypopituitarism and adrenal insufficiency)
 

	Grade 3 or 4	Withhold or permanently discontinue 		
Hyperthyroidism	Grade 2	Continue	
 
Treat with nonselective beta-blockers (e.g. propranolol) or thionamides as appropriate
 
	
 
Monitor for signs and symptoms of thyroid disorders.
 

	Grade 3 or 4	Withhold or Permanently discontinue 		

Immune-related AEs	Toxicity grade or conditions (CTCAEv4.03)	Action taken to pembrolizumab	irAE management with corticosteroid and/or other therapies	Monitor and follow-up

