NOTES: Non-irAE will be managed as appropriate, following clinical practice recommendations.

1. AST/ALT: >3.0 - 5.0 x ULN if baseline normal; >3.0 - 5.0 x baseline, if baseline abnormal; bilirubin:>1.5 - 3.0 x ULN if baseline normal; >1.5 - 3.0 x baseline if baseline abnormal
2. AST/ALT: >5.0 to 20.0 x ULN, if baseline normal; >5.0 - 20.0 x baseline, if baseline abnormal; bilirubin:>3.0 - 10.0 x ULN if baseline normal; >3.0 - 10.0 x baseline if baseline abnormal
3. AST/ALT: >20.0 x ULN, if baseline normal; >20.0 x baseline, if baseline abnormal; bilirubin: >10.0 x ULN if baseline normal; >10.0 x baseline if baseline abnormal
4. The decision to withhold or permanently discontinue pembrolizumab is at the discretion of the investigator or treating physician. If control achieved or ≤ Grade 2, pembrolizumab may be resumed. .
5. Events that require discontinuation include but are not limited to: encephalitis, and other clinically important irAEs (eg. Vasculitis and sclerosing cholangitis).

[figure not shown]

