### 6.12.4. Supportive Care Guidelines for Pembrolizumab

Subjects should receive appropriate supportive care measures as deemed necessary by the treating investigator. Suggested supportive care measures for the management of AEs with potential immunologic etiology are outlined along with the dose modification guidelines in [6.5.2](#). Where appropriate, these guidelines include the use of oral or intravenous treatment with corticosteroids, as well as additional anti-inflammatory agents if symptoms do not improve with administration of corticosteroids. Note that several courses of steroid tapering may be necessary as symptoms may worsen when the steroid dose is decreased. For each disorder, attempts should be made to rule out other causes such as metastatic disease or bacterial or viral infection, which might require additional supportive care. The treatment guidelines are intended to be applied when the investigator determines the events to be related to pembrolizumab.

Note: If after the evaluation the event is determined not to be related, the investigator does not need to follow the treatment guidance. Refer to [Table 5](#) for guidelines regarding dose modification and supportive care.

It may be necessary to perform conditional procedures such as bronchoscopy, endoscopy, or skin photography as part of evaluation of the event.

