**12.5.2.1. Rechallenge Following Liver Stopping Events that are Possibly Related to Study Treatment**

Following drug-induced liver injury, **drug rechallenge is associated with a 13% mortality across all drugs in prospective studies.** Clinical outcomes vary by drug, with nearly 50% fatality with halothane readministered within one month of initial injury. However, some drugs seldom result in recurrent liver injury or fatality.

Risk factors for a fatal drug rechallenge outcome include:

- hypersensitivity with initial liver injury (e.g. fever, rash, eosinophilia)
- jaundice or bilirubin >2xULN with initial liver injury (direct bilirubin >35% of total)
- subject currently exhibits severe liver injury defined by: ALT  $\geq$ 3xULN, bilirubin  $\geq$ 2xULN (direct bilirubin >35% of total), or INR  $\geq$ 1.5
- serious adverse event or fatality has earlier been observed with drug challenges
- evidence of drug-related preclinical liability (e.g. reactive metabolites; mitochondrial impairment)

Rechallenge refers to resuming study treatment following drug induced liver injury (DILI). Because of the risks associated with rechallenge after DILI this should only be considered for a subject for whom there is compelling evidence of benefit from a critical or life-saving medicine, there is no alternative approved medicine available, and a benefit:risk assessment of rechallenge is considered to be favourable.

Approval by GSK for rechallenge with study treatment can be considered where:

- Investigator requests consideration of rechallenge with study treatment for a subject who is receiving compelling benefit with study treatment that exceeds risk, and no effective alternative therapy is available.
- Ethics Committee or Institutional Review Board approval for rechallenge with study treatment must be obtained, as required.
- If the rechallenge is approved by GSK Medical Governance in writing, the subject must be provided with a clear description of the possible benefits and risks of study treatment administration, including the possibility of recurrent, more severe liver injury or death.
- The subject must also provide signed informed consent specifically for the rechallenge with study treatment. Documentation of informed consent must be recorded in the study chart.
- Study treatment must be administered at the dose specified by GSK.

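### For an asymptomatic ALT rise between 3 and 5 x ULN, Table 5 and Section 6.5.2 require a hold with corticosteroids, Appendix 5 permits continued dosing, and no text shown says which prevails

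*Protocol*

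**What the plan says.** Section 6 of the protocol defines study treatment as belantamab mafodotin and pembrolizumab together.

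**Table 5 (Section 6.5.2).** The row is labelled "AST / ALT elevation or Increased Bilirubin". Note 1 gives the Grade 2 transaminase range as "AST/ALT: >3.0 - 5.0 x ULN if baseline normal; >3.0 - 5.0 x baseline, if baseline abnormal". The action on pembrolizumab is to withhold, and the management column says "Administer corticosteroids (initial dose of 0.5 to 1 mg/kg prednisone or equivalent) followed by taper". Grade 3, "AST/ALT: >5.0 to 20.0 x ULN, if baseline normal; >5.0 - 20.0 x baseline, if baseline abnormal", and Grade 4 call for permanent discontinuation.

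**Section 6.5.2, attribution paragraph.** For events listed in Table 5, whether blamed on the combination or on either drug alone, "both interventions must be held according to the criteria in" that table.

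**Text that narrows Table 5.** The next paragraph of Section 6.5.2 ties holding both drugs to events considered immune-related. The notes to Table 5 leave events that are not immune-related to clinical practice. Section 6.12.4 says "The treatment guidelines are intended to be applied when the investigator determines the events to be related to pembrolizumab".

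**Appendix 5, Section 12.5.1.** ALT of at least 3 but below 5 x ULN, with bilirubin below 2 x ULN, no relevant symptoms and weekly monitoring possible, is a monitoring event: "Subject can continue study treatment". The medical monitor is told within 24 hours and liver chemistries are repeated weekly. ALT of 5 x ULN or more is a stopping event. So is ALT of 3 x ULN or more that lasts 4 weeks, or that comes with symptoms, raised bilirubin, raised INR or no possibility of weekly monitoring.

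**Restart.** Section 5.4.1.2 and Appendix 5 allow restart or rechallenge on conditions. For events possibly related to treatment, Section 12.5.2.1 begins "Approval by GSK for rechallenge with study treatment can be considered where" and lists them.

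**The concern.** Both sets of rules start from the same laboratory result, and a site may reach either one first. One reader withholds both drugs and starts steroids. Another continues dosing with weekly tests. Each can point to protocol text.

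Hepatotoxicity is listed in Section 4.6.1 (Table 2) as a potential overlapping toxicity of the two drugs, so this is a safety instruction and should have one reading. It also bears on the data. Exposure and steroid use could differ between sites for the same values. In Part 1, a hold that delays Cycle 2 by more than 14 days because of treatment-related toxicity is itself a dose-limiting toxicity (Section 4.2.3.1).

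**Working it through.** The plan states no figure on this point that could be reproduced. The check applies both rule sets to the same values.

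**Inputs.** Table 5 and notes 1 to 3; the Appendix 5 stopping and monitoring criteria; the entry limit for AST and ALT of 2.5 x ULN (Table 3), which allows an abnormal baseline. Bilirubin is 1 x ULN throughout, and the subject has no symptoms and can be monitored weekly.

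| Baseline ALT | On-study ALT | Table 5 | Appendix 5 |
|---|---|---|---|
| normal | 4 x ULN | Grade 2: withhold, steroids | can continue, notification and weekly tests |
| normal | 4 x ULN, persisting 4 weeks | Grade 2: withhold, steroids | stopping event |
| normal | exactly 5.0 x ULN | Grade 2: withhold, steroids | stopping event |
| normal | 6 x ULN | Grade 3: permanently discontinue | stopping event, conditional rechallenge |
| 2.0 x ULN | 5.5 x ULN | below Grade 2 | stopping event |
| 2.5 x ULN | 7 x ULN | below Grade 2 | stopping event |

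**First row: the core conflict.** The Table 5 column itself addresses pembrolizumab. The attribution paragraph of Section 6.5.2 extends the hold to both drugs, and the Appendix 5 permission also covers both. There are two possible scopes for Table 5:
- If it applies to any transaminase rise, the conflict covers the whole asymptomatic band above 3 and below 5 x ULN.
- If it applies only to immune-related or pembrolizumab-related rises, the conflict remains for those, because Appendix 5 carves out no such events.

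**Above 5 x ULN.** With normal baseline both texts stop treatment. Table 5 makes the stop permanent. Section 5.4.1.2 and Appendix 5 leave a route back without mentioning Table 5.

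**Abnormal baseline.** Table 5 limits convert to ULN as multiple x baseline:
- Baseline 2.0 x ULN: Grade 2 above 3.0 x 2.0 = 6.0 x ULN; Grade 3 above 5.0 x 2.0 = 10 x ULN.
- Baseline 2.5 x ULN: Grade 2 above 3.0 x 2.5 = 7.5 x ULN; Grade 3 above 5.0 x 2.5 = 12.5 x ULN.
- The Appendix 5 absolute limit is 5 x ULN at any baseline. ALT 5.5 x ULN from a baseline of 2.0 is 5.5 / 2.0 = 2.75 x baseline, and 7 x ULN from 2.5 is 7 / 2.5 = 2.8 x baseline. Both are below Table 5 Grade 2.

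**Possible effect on a dose-limiting toxicity.** Table 5 starts the steroid taper at Grade 1 or less, continues it for at least 4 weeks, and lets pembrolizumab resume after it. Suppose a Grade 2 rise judged treatment-related is found at the Day 8 visit.
- If it resolved at once, the earliest resumption would be Day 8 + 28 = Day 36. Cycle 2 is due on Day 22, so the delay is 36 - 22 = 14 days.
- Each day needed to return to Grade 1 is added, so one day takes the delay past the 14-day limit.
- Under Appendix 5 the same subject could be dosed on Day 22 with no delay.

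In Table 1, 0 of 3 means escalate and 1 of 3 means stay. This is one scenario, and escalation decisions also use all other safety data.

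**The case against.** **Scope.** Table 5 sits under headings about immune-related and pembrolizumab-related events, and three further sentences confine it to such events. The attribution paragraph can be read as settling which drug is blamed, not whether the event is immune-related. A rise with another cause would then fall outside Table 5. This is a fair reading and it shrinks the conflict. It does not remove it, because Appendix 5 makes no exception for immune-related rises. The attribution paragraph also sits badly with Section 6.12.4, which makes relation to pembrolizumab the condition.

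**Permission against obligation.** Appendix 5 only allows continuation, and a site that holds breaks neither text. It must also call the medical monitor within 24 hours, which is a chance to sort the matter out. Both points stand. But a site that relies on the permission breaks the hold, and nothing warns it.

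**Rechallenge.** Appendix 5 allows it only if the protocol permits and the sponsor's medical governance approves, with ethics approval where required and separate signed consent. No site reaches it by opening the wrong page. What remains is a missing cross-reference to the permanent stop in Table 5.

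**Abnormal baseline.** Below its Grade 2, Table 5 is silent, and silence does not tell a site to continue. Only Appendix 5 gives an instruction there. This is a difference of triggers, not a contradiction.

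**Dose-limiting toxicity.** The liver criterion in Section 4.2.3.1 points to Section 5.4.1.1 alone and is unambiguous. Any effect comes through the delay criterion.

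**Unseen text.** Figure 3, the liver algorithm, is not shown and might link the rules.

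**Conclusion.** The contradiction is real for an asymptomatic subject with normal baseline, ALT above 3 and below 5 x ULN and bilirubin below 2 x ULN: a required hold of both drugs with corticosteroids on one side, permitted continuation of both on the other. Its extent depends on the scope of Table 5, from immune-related or pembrolizumab-related rises only up to the whole band. The rechallenge route and the two reference values are lesser mismatches. The conclusion assumes that Figure 3 contains no rule of precedence.

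A reader might infer more than the documents support:
- That the same subject could be held, continued or stopped. At one time point the two texts give at most two actions. Stopping enters through a further condition such as persistence, symptoms, raised bilirubin or a higher ALT.
- That Appendix 5 lets dosing go on unsupervised. It requires notification and weekly tests.
- That raised AST among the events seen in at least 30% of subjects in Part 2 of the first-in-human study measures the problem. That figure carries no grade and is not ALT in this band. The documents give no frequency for the band.
- That exposure or liver-event rates could not be interpreted. What is supported is that dosing, steroid use and possibly delay-based dose-limiting toxicities could differ between sites.

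**What to change.** Reconcile the Table 5 liver row and its notes, the attribution and holding paragraphs of Section 6.5.2, and Section 6.12.4 with Section 5.4.1.2 and Appendix 5 (Sections 12.5.1 to 12.5.2.1). Specifically:

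1. State in both places which rule takes precedence for ALT between 3 and 5 x ULN, and whether that depends on the event being immune-related or related to pembrolizumab.
2. Cross-refer the permanent discontinuation in Table 5 to the restart and rechallenge sections, and say whether that route is open for such events.
3. State how the ULN-based and baseline-based limits work together when baseline is abnormal, and settle the value of exactly 5.0 x ULN, which now falls on different sides in the two texts.
4. Check that Figure 3 agrees.

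The sponsor decides the clinical content. The requirement here is only that one set of laboratory values leads to one instruction. The cost is amendment wording and a memo to sites, with no added visits, tests or subjects.

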**12.5.2. Liver Safety Drug Restart or Rechallenge Guidelines**

If subject meets liver chemistry stopping criteria do not restart/rechallenge subject with study treatment unless:

- GSK Medical Governance approval **is granted** (as described below),
- Ethics and/or IRB approval is obtained, if required, and
- Separate consent for treatment restart/rechallenge is signed by the subject

If GSK Medical Governance approval to restart/rechallenge subject with study treatment **is not granted**, then subject must permanently discontinue study treatment and may continue in the study for protocol-specified follow up assessments

**12.5.2.1. Rechallenge Following Liver Stopping Events that are Possibly Related to Study Treatment**

Following drug-induced liver injury, **drug rechallenge is associated with a 13% mortality across all drugs in prospective studies.** Clinical outcomes vary by drug, with nearly 50% fatality with halothane readministered within one month of initial injury. However, some drugs seldom result in recurrent liver injury or fatality.

Risk factors for a fatal drug rechallenge outcome include:

- hypersensitivity with initial liver injury (e.g. fever, rash, eosinophilia)
- jaundice or bilirubin >2xULN with initial liver injury (direct bilirubin >35% of total)
- subject currently exhibits severe liver injury defined by: ALT  $\geq$ 3xULN, bilirubin  $\geq$ 2xULN (direct bilirubin >35% of total), or INR  $\geq$ 1.5
- serious adverse event or fatality has earlier been observed with drug challenges
- evidence of drug-related preclinical liability (e.g. reactive metabolites; mitochondrial impairment)

Rechallenge refers to resuming study treatment following drug induced liver injury (DILI). Because of the risks associated with rechallenge after DILI this should only be considered for a subject for whom there is compelling evidence of benefit from a critical or life-saving medicine, there is no alternative approved medicine available, and a benefit:risk assessment of rechallenge is considered to be favourable.

Approval by GSK for rechallenge with study treatment can be considered where:

- Investigator requests consideration of rechallenge with study treatment for a subject who is receiving compelling benefit with study treatment that exceeds risk, and no effective alternative therapy is available.
- Ethics Committee or Institutional Review Board approval for rechallenge with study treatment must be obtained, as required.
- If the rechallenge is approved by GSK Medical Governance in writing, the subject must be provided with a clear description of the possible benefits and risks of study treatment administration, including the possibility of recurrent, more severe liver injury or death.
- The subject must also provide signed informed consent specifically for the rechallenge with study treatment. Documentation of informed consent must be recorded in the study chart.
- Study treatment must be administered at the dose specified by GSK.
- Subjects approved by GSK Medical Governance for rechallenge with study treatment must return to the clinic twice a week for liver chemistry tests until stable

liver chemistries have been demonstrated and then standard laboratory monitoring may resume as per protocol.

- If after study treatment rechallenge, subject meets protocol-defined liver chemistry stopping criteria, study treatment should be permanently discontinued.
- GSK Medical Monitor, and the Ethics Committee or Institutional Review Board as required, must be informed of the subject's outcome following study treatment rechallenge.
- GSK to be notified of any adverse events, as per Section [7.3.1](#).

#### **12.5.2.2. Restart Following Transient Resolving Liver Stopping Events NOT Related to Study Treatment**

Restart refers to resuming study treatment following liver stopping events in which there is a clear underlying cause (other than DILI) of the liver event (e.g. biliary obstruction, pancreatic events, hypotension, acute viral hepatitis). Furthermore, there should be no evidence of alcoholic hepatitis or hypersensitivity, and the study treatment should not be associated with HLA markers of liver injury.

Approval by GSK for study treatment restart can be considered where:

- Investigator requests consideration for study treatment restart if liver chemistries have a clear underlying cause (e.g., biliary obstruction, hypotension and liver chemistries have improved to normal or are within 1.5 x baseline and ALT <3xULN).
- Possible study treatment-induced liver injury has been excluded by the investigator and the study team. This includes the absence of markers of hypersensitivity (otherwise unexplained fever, rash, eosinophilia). Where a study treatment has an identified genetic marker associated with liver injury (e.g. lapatinib, abacavir, amoxicillin/clavulanate), the presence of the marker should be excluded. If study treatment-related liver injury cannot be excluded, the guidance on rechallenge in Section [12.5.2](#) will apply.
- There is no evidence of alcoholic hepatitis.
- Ethics Committee or Institutional Review Board approval of study treatment restart must be obtained, as required.
- If restart of study treatment is approved by GSK Medical Governance in writing, the subject must be provided with a clear description of the possible benefits and risks of study treatment administration, including the possibility of recurrent, more severe liver injury or death.
- The subject must also provide signed informed consent specifically for the study treatment restart. Documentation of informed consent must be recorded in the study chart.
- Study treatment must be administered at the dose specified by GSK.

- Subjects approved by GSK Medical Governance for restarting study treatment must return to the clinic once a week for liver chemistry tests until stable liver chemistries have been demonstrated and then laboratory monitoring may resume as per protocol.
- If after study treatment re-start, subject meets protocol-defined liver chemistry stopping criteria, follow usual stopping criteria instructions.
- GSK Medical Monitor, and the Ethics Committee or Institutional Review Board as required, must be informed of the subject's outcome following study treatment restart.
- GSK to be notified of any adverse events, as per Section [7.3.1](#).

